Oesophageal temperature accurately reflects core temperature (5) when a probe is positioned in the lower oesophagus (excluding open heart or lung surgery). However, the position of this probe must accurately be in the lower third of the oesophagus, lest a higher location is influenced by the cooler tracheal temperature (6-9). Compared to an adult, the short distance between the stomach, lower and middle oesophagus in a child makes reliable placement challenging. In order to achieve the precise placement of oesophageal temperature probes in adults and children, some formulas (10, 11) have been devised with varying success but none is perfect and accurate oesophageal temperature probe placement remains elusive, limiting the usefulness of the site.

The nasopharynx receives a good blood supply via the external carotid artery and therefore could correlate well with core temperature. The nasopharyngeal temperature probe confers the advantage of simplicity of placement compared to its oesophageal counterpart. The value of nasopharyngeal temperature's correlation with that of the core is generally regarded as accurate (12-14) in adults. In children undergoing anaesthesia often uncuffed endotracheal tubes are utilized, as historically in paediatric anaesthesia there have been concerns about subglottic stenosis and postoperative stridor (15) but to date there is no evidence that newer Microcuff® tubes are any less safe in children than uncuffed tubes (19). The use of uncuffed tubes is in direct contrast to adults, in whom cuffed endotracheal tubes are placed by anaesthetists. In the paediatric population very little evidence exists, although in small, poor quality trials findings are favourable for nasopharyngeal temperature comparisons to core (16). When a patient is ventilated during general anaesthesia, a humidity and moisture exchange filter (HMEF) assists in warming inspired gases administered from an anaesthetic machine, but does so incompletely (not achieving body temperature). With an uncuffed

endotracheal tube an escape of ventilated gases from the trachea upwards towards the mouth and nose occurs via the nasopharynx. With a temperature that is lower than body temperature, even at low flows, (17) these gases could possibly have a cooling effect on temperature in the nasopharynx (18). The question remains, thus, whether or not nasopharyngeal temperature is influenced by the cooling effects of these escaped gases or not.

Study objectives

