This study will seek to find an agreement of methods (lower oesophageal and nasopharyngeal sites) to measure temperature in children undergoing general anaesthesia with an endotracheal tube that has a leak. This is an important question to answer because it is not known whether or not oesophageal and nasopharyngeal temperatures correlate in children ventilated with an uncuffed endotracheal tube, and would allow clinicians to confidently use the more feasible nasopharyngeal temperature probes if this were the case.

Study Design

Prospective, unblinded, cross-sectional (observational) agreement study

Approval will be obtained from the Research Ethics Committee

Written parental informed consent will be obtained prior to investigation. Parents will be informed of their right to withdraw at any stage of the trial without compromising their clinical care.

Inclusion criteria

Age: 8 months to 7 years

Patient requires general anaesthesia with endotracheal intubation for a procedure assisted by radiography (e.g. line insertion, line change)

Patient requires chest radiograph for procedure

Expected anaesthetic time more than 30 minutes

Exclusion criteria

No written parental written consent

Known oesophageal pathology (e.g. tracheo-oesophageal fistula, oesophageal strictures, oesophageal varices, oesophageal atresia)

Known base of skull or midface fractures

Previous gastric bypass surgery or nasal surgery

Known coagulopathy

Previous alkaline ingestion

High aspiration risk

Significant respiratory co-morbidity requiring anticipated peak airway pressures $> 25 \text{ cmH}_2\text{O}$

ASA 4 – 5

Tracheostomy in situ

Severe sepsis or septic shock or other other condition (such as bronchopulmonary fistula) that precludes use of tidal volume ventilation over 7 ml/kg

Known airway abnormalities (e.g. subglottic stenosis) that preclude placement of a MicroCuff® endotracheal tube

Oesophageal or nasopharyngeal probe contraindicated for reasons related to surgery / procedure

Feasibility of study/ number of patients

Statistical advice and analysis has been sought from the Great Ormond Street Hospital/ Institute for Child Health (ICH) statistical support team. 100 patients would suffice to be able to estimate agreement between methods, giving a 95% CI about $+/- (0.34 \times \text{standard deviation})$.

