The insertion of the oesophageal probe is a safe procedure, with very few side-effects reported in the literature. Rarely has an oesophageal temperature probe been inadvertently inserted intratracheally (31). If this were to occur, early diagnosis would be possible due to accompanying radiography, noting the probe to cross the carina. Rarely will oesophageal probe insertion fail, in which case recruitment into the study will terminate.

Statistics and data analysis

We consider a clinically unacceptable difference as a difference of greater than 0.5°C between methods.

The study recruitment rate will be assessed by recording patients successfully entered into the study as well as those for whom parental consent was not achieved. Demographic data will be appropriately recorded and analysed in terms of means and medians. Temperature measurements with the oesophageal probe will be compared to temperature measurements with the nasopharyngeal probe and mean differences, standard deviations, and 95% confidence intervals will be calculated and tabulated. Bland-Altman plots of the esophageal-nasopharyngeal temperature differences will be drawn. Differences will be checked for normality. Differences against mean will also be checked for variability (making sure that differences do not increase with mean). Linear regression analysis shall be utilized with scatter plot diagrams and r values calculated. A paired t-test will be performed to exclude systematic bias. Endotracheal leak, as measured by spirometry and fractional volume loss, will be measured, analysed and tabulated for means and standard deviations. It is anticipated that a clinically audible leak will correspond to a FVL of approximately 12.4 – 29.3% (based on data received directly from study author regarding IQR from a previous study (32)) for 50% of patients.

After the study has been completed we also plan to do a subgroup analysis for agreement between methods on 2 subgroups of patients: (1) those with FVL < 21.1% (2) those with FVL > 21.1%. This is in order to determine if there is any potential effect of leak size that might affect temperature differences.

Data handling

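### The paired t-test is asked to exclude systematic bias, which a non-significant result cannot do; the consequence is confined to biases well below 0.5°C

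*Combined protocol and SAP*

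**What the plan says.** The Statistics and data analysis section gives the test a written purpose: "A paired t-test will be performed to exclude systematic bias". It attaches no significance level, sidedness, power, margin or equivalence rule to the test, and does not say whether the test applies with the cuff inflated, with it deflated, or both.

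The same section sets one clinical threshold, "We consider a clinically unacceptable difference as a difference of greater than 0.5°C between methods", but does not connect it to the t-test. It also provides the estimates that bear on bias: "mean differences, standard deviations, and 95% confidence intervals will be calculated and tabulated", together with Bland-Altman plots. Later it adds a "subgroup analysis for agreement between methods on 2 subgroups of patients", split at a fractional volume loss (FVL) of 21.1%, and does not say whether the t-test is repeated there.

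The Background explains why a mean shift is of interest. Gas leaking past the tube is cooler than the body, and "these gases could possibly have a cooling effect on temperature in the nasopharynx"; the open question is "whether or not nasopharyngeal temperature is influenced by the cooling effects of these escaped gases or not".

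The Feasibility section justifies the sample size by precision: "100 patients would suffice to be able to estimate agreement between methods, giving a 95% CI about" ±0.34 SD.

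**The concern.** A paired t-test asks whether the data are inconsistent with a mean difference of exactly zero. Non-significance means that zero has not been rejected. It does not mean that other values have been. Used to exclude bias, the test also works in the wrong direction: for a given non-zero bias, noisier differences make non-significance more likely, so bias would be called absent more often where the probes agree less well. If the true bias is exactly zero, the chance of non-significance stays at 95% whatever the SD.

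Cooling of the nasopharynx by leaked gas would form part of the mean oesophageal-minus-nasopharyngeal difference, so the sentence touches the study question. What is at stake is a report that says bias was excluded beside a confidence interval that still includes a real, though small, bias. The reverse error is also possible: with 100 pairs the test can flag a bias that is trivial against the plan's own 0.5°C.

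**Working it through.** **Inputs from the documents:** n = 100 (Feasibility section); threshold 0.5°C (Statistics section). **Assumptions, because the documents give no values:** two-sided 5% level; SD of the paired differences 0.20 to 0.50°C; true bias 0.1°C or 0.05°C; about 50 children per FVL subgroup (even split).

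**The plan's own figure.** The half-width of a 95% interval for one limit of agreement is 1.96 × √(3/n) × SD. At n = 100 this is 1.96 × √0.03 = 0.339 SD, which reproduces the stated 0.34 SD. The sample size therefore rests on the limits of agreement, not on the t-test. For the mean difference the half-width is t(0.975; 99)/√100 = 1.984/10 = 0.198 SD.

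**Chance of a non-significant test.** With T noncentral t, df = n − 1 and noncentrality bias × √n / SD, the chance is P(|T| < t(0.975; n − 1)). For example, at n = 100, bias 0.1°C and SD 0.40°C the noncentrality is 0.1 × 10 / 0.40 = 2.5, and the chance is 0.303.

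**Largest bias left open.** A result just short of significance has an observed mean difference of one half-width, so its interval runs from zero to two half-widths: 2 × 0.1984 = 0.397 SD at n = 100. At n = 50 it is 2 × 2.010/√50 = 0.568 SD.

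**Share of children beyond 0.5°C.** With normal differences and bias 0.1°C this is P(Z > 0.4/SD) + P(Z < −0.6/SD).

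| SD (°C) | Non-significant, n = 100, bias 0.1°C | Interval can reach, n = 100 (°C) | Children beyond 0.5°C | Non-significant, n = 50 | Interval can reach, n = 50 (°C) |
|---|---|---|---|---|---|
| 0.20 | 0.1% | 0.08 | 2% | 7% | 0.11 |
| 0.25 | 2% | 0.10 | 6% | 21% | 0.14 |
| 0.30 | 9% | 0.12 | 11% | 36% | 0.17 |
| 0.40 | 30% | 0.16 | 23% | 59% | 0.23 |
| 0.50 | 49% | 0.20 | 33% | 72% | 0.28 |

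**The other direction.** At n = 100, bias 0.05°C and SD 0.20°C the noncentrality is 0.05 × 10 / 0.20 = 2.5. The test is significant in 1 − 0.303 = 70% of trials, for a bias one tenth of 0.5°C.

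**Where the problem stops.** The interval after a non-significant test reaches 0.5°C only if the observed SD exceeds 0.5/0.397 = 1.26°C at n = 100, or 0.5/0.568 = 0.88°C at n = 50.

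**What the planned interval shows.** Trials whose interval lies wholly below the true 0.1°C make up 2.5% of all trials, and at these SDs practically all of them are non-significant. So among non-significant trials the interval still contains 0.1°C in about 1 − 0.025/0.303 = 92% at SD 0.40°C and 1 − 0.025/0.492 = 95% at SD 0.50°C. The interval would usually contradict a statement that bias had been excluded.

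**The case against.** The best reply is that the same paragraph already handles the matter. The 95% interval for the mean difference carries the same information as a two-sided 5% paired t-test and also shows how large a bias remains possible. The SD and the Bland-Altman plots would expose poor agreement whatever the test said: at SD 0.50°C and bias 0.1°C, a third of children beyond 0.5°C would be plain to see. The biases used here are a tenth and a fifth of the only threshold in the plan, and the documents name neither as important. All of this stands, and it limits the weight of the point. It does not make the sentence correct. If the wording was only meant as a check for bias, rewording loses nothing.

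A reader might infer more than the documents support:

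- *That the report will declare cooling absent.* The plan ties no reporting rule or conclusion to the test, so a misleading statement is possible, not scheduled. The mean difference may also include a fixed offset between the two sites, so a t-test in one cuff condition is not the plan's statement on cooling.
- *That neither test result says whether the bias matters.* Across the assumed SDs, a non-significant result bounds the bias at 0.20°C or less (n = 100) or 0.28°C or less (n = 50), below 0.5°C in both cases.
- *That the FVL subgroups will be misjudged.* The plan does not assign the t-test to them, and the even split is an assumption.

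**Conclusion.** The sentence is wrong as written, and the point is minor. A non-significant paired t-test cannot exclude systematic bias. Under the stated assumptions it would miss a 0.1°C bias in 9% to 49% of trials at SDs of 0.30 to 0.50°C, and in 2% or fewer at SDs of 0.25°C or below. What it leaves open is small: at most 0.08 to 0.20°C over SDs of 0.20 to 0.50°C with 100 children.

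The algebra (0.397 SD, and 1.26°C as the SD at which 0.5°C stays open) needs only n = 100 and the two-sided 5% level. The percentages depend on the assumed SD and bias as well. The documents do not support the stronger reading that the agreement analysis as a whole fails, or that a clinically unacceptable mean bias would probably be missed.

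**What to change.** In the Statistics and data analysis section, replace the t-test sentence with:

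> Systematic bias will be estimated by the mean difference (oesophageal minus nasopharyngeal) with its 95% CI, read against 0.5°C; the paired t-test is supportive, and a non-significant result will not be taken as absence of bias.

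Use the same wording for the FVL subgroups if the test is applied there.

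The cost is one sentence. No extra patients, data or analyses are needed, because the mean difference and its interval are already to be tabulated. The downside is that the report can no longer say bias was excluded, only that it is no larger than the confidence bound.

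The wording on limits of agreement, the role of r and the labelling of ±0.34 SD are separate clarifications and not part of this point.

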Once the initial radiograph has been taken (timing of which shall be dictated by the surgical team as this radiograph will assist with the procedure), the intervertebral space between the 8th and 9th thoracic vertebrae will be identified and the distance between the end of the oesophageal probe and this landmark will be measured. The position of the end of the temperature probe will be adjusted to the level of T8/ T9, which corresponds to the lower third of the oesophagus.

The anaesthetic gas mixture flow will be set at 2L /min in order to standardize the flow of this potentially cooling factor between patients. The anaesthetist will set the ventilator mode to volume control ventilation (VCV) without leak compensation with a Peak End Expiratory Pressure (PEEP) of 5 and a tidal volume of 7 – 9 ml/kg. The inspiratory: expiratory (I:E) ratio will be set to 1:2. Approximately 1 minute following satisfactory positioning of the temperature probe, the temperature of the oesophageal and nasopharyngeal probes will be recorded over a period of 20 breath cycles (approximately 1 minute), while the ventilator's

spirometric equipment will be utilized to measure expired tidal volume and peak airway pressure..

The endotracheal tube cuff will now be deflated to allow an anaesthetic gas leak, thus simulating the use of an uncuffed endotracheal tube. The volume of air in the cuff will be adjusted by the anaesthetist to achieve a clinically soft audible leak (whilst on the ventilator). Temperature and spirometry measurements will recommence approximately 1 minute hereafter (simulating an uncuffed endotracheal tube scenario), again over a period of 20 breath cycles. Once this is completed the anaesthetist will use their discretion whether or not they wish to fully re-inflate (with cuff manometry) the endotracheal tube cuff or not for the remainder of the procedure.

As is usual during anaesthesia, standard body warming measures (aiming for normothermia) will be taken, guided by the measured temperatures.

Data collection

The following data will be collected:

Demographics – including date of procedure, date of birth, age, height, ASA status

Initial distance that oesophageal probe is inserted, based on formula described above

Distance of oesophageal probe tip away from T8/T9 intervertebral space

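### The plan asks whether leak size affects the temperature difference but specifies only separate agreement results either side of 21.1% FVL, with no estimate of a leak effect

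*Combined protocol and SAP*

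**What the plan says.** All the relevant analysis text is in the Statistics and data analysis section.

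- **Subgroup analysis:** "we also plan to do a subgroup analysis for agreement between methods on 2 subgroups of patients: (1) those with FVL < 21.1" (in %); the second group is those above 21.1%.
- **Its purpose:** "This is in order to determine if there is any potential effect of leak size that might affect temperature differences".
- **Statistics for the probe comparison:** "mean differences, standard deviations, and 95% confidence intervals will be calculated and tabulated". Bland-Altman plots and a paired t-test for systematic bias are also planned.
- **Regression:** "Linear regression analysis shall be utilized with scatter plot diagrams and r values calculated". No outcome or predictor is named. The sentence sits among the comparisons of the two probes, before that section first mentions FVL.
- **FVL itself:** "will be measured, analysed and tabulated for means and standard deviations".
- **Expected leak:** "It is anticipated that a clinically audible leak will correspond to a FVL of approximately 12.4 – 29.3" (in %), given as an interquartile range from another study.
- **Acceptability threshold:** "We consider a clinically unacceptable difference as a difference of greater than 0.5°C between methods".

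Under Patient management and intervention, the leak is titrated, not assigned: "The volume of air in the cuff will be adjusted by the anaesthetist to achieve a clinically soft audible leak".

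**The concern.** The question concerns an effect: does the temperature difference change as the leak gets larger? The method attached to it is two agreement analyses, one per group. These show whether agreement is acceptable at smaller leaks and at larger leaks, which is useful but is a different question. Neither result estimates how much the difference changes with leak, and the plan does not say how the two will be combined into a conclusion.

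The risk is that leak size will be judged informally, for example because one group shows a significant bias and the other does not. Two groups with identical true behaviour can easily differ in that way. The risk also runs the other way, since a real but modest effect can be missed. FVL is measured on a continuous scale in every child, and cutting it in two discards information if the effect is graded.

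The cooling effect of escaping gas is the question the Background section raises, so this analysis bears on the study's rationale even though it is secondary.

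**Working it through.** **Inputs from the protocol:** n = 100 and a CI of ±0.34 SD (Feasibility of study/ number of patients); FVL interquartile range 12.4–29.3%, cut-point 21.1% and threshold 0.5°C (Statistics and data analysis).

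**Assumptions, because the documents give no values:** SD of the temperature difference 0.2, 0.3 or 0.4°C; FVL normal with mean 21.1%; 50 children per group; the effect sizes and correlations stated below.

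**1. The plan's own figure.** The half-width of the 95% CI for a limit of agreement is 1.96 × √(3/n) SD. At n = 100 it is 1.96 × √0.03 = 0.339 SD, which reproduces 0.34. In a group of 50 it is 1.96 × √0.06 = 0.480 SD.

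**2. Reading two separate bias tests.** Suppose both groups of 50 share a true bias of 0.2 SD. Each test is significant with probability 0.293, so exactly one is significant with probability 2 × 0.293 × 0.707 = 0.41. At 0.28 SD the figure is 50%, and at 0.4 SD it is 31%. Requiring instead that the two 95% CIs do not overlap needs a difference of 2 × 1.96/√50 = 0.554 SD. That corresponds to a significance level of about 0.006. It has 51% power at a true difference of 0.56 SD, where a direct contrast has 80%.

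**3. Reading two limits-of-agreement verdicts.** This applies only if a group passes when its limits lie within ±0.5°C, a rule the plan does not state. With no leak effect and zero bias, the two groups disagree in 5% of studies at SD 0.20°C, 50% at 0.24°C, 5% at 0.30°C and 0% at 0.40°C. The problem is confined to true limits near ±0.5°C.

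**4. Precision of a direct contrast.** 1.96 × SD × √(1/50 + 1/50) = 0.392 SD, which is ±0.08, ±0.12 and ±0.16°C at SD 0.2, 0.3 and 0.4°C.

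**5. Precision of a slope.** The SD of FVL is (29.3 − 12.4)/(2 × 0.6745) = 16.9/1.349 = 12.53 points. At SD 0.3°C the half-width is about 1.96 × 0.3/(12.53 × √100) = 0.0047°C per point, or 0.047°C per 10 points. The normal model gives 4.6% negative FVL values. Simulation with t-based intervals gives ±0.048 to ±0.053°C per 10 points, depending on whether those values are kept, set to zero or redrawn. At SD 0.2°C it is ±0.032 to ±0.035, and at SD 0.4°C ±0.064 to ±0.071. Across the interquartile range (× 1.69) the SD 0.3°C figure is ±0.08 to ±0.09°C.

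**6. Information lost by the split.** For a normal predictor cut at its median with a linear effect, the loss is 1 − 2/π = 0.363. The midpoint of the stated interquartile range is (12.4 + 29.3)/2 = 20.85%, so 21.1% is plausibly near the median.

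**7. Power.** Mean cooling of 0.10°C, linear in FVL (0.10 × FVL/21.1), n = 100, two-sided 5%, 200,000 simulated studies per setting:

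| SD (°C) | Split, negative FVL kept | Continuous, kept | Split, redrawn | Continuous, redrawn |
|---|---|---|---|---|
| 0.2 | 63% | 83% | 56% | 75% |
| 0.3 | 34% | 49% | 29% | 42% |
| 0.4 | 21% | 31% | 19% | 26% |

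If the truth is instead a 0.10°C step exactly at 21.1%, at SD 0.3°C the split does better, about 38% against 26%.

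**8. Confounding.** Take no leak effect, SD 0.3°C, age correlated 0.3 with FVL, and the difference shifting 0.10°C per SD of age. The unadjusted slope is then falsely significant in 17% of studies and the split contrast in 13%. Adjusting the slope for age returns it to 5%. With a 0.05°C shift the unadjusted figures are 8% and 7%. With correlation 0.5 and a 0.10°C shift they are 39% and 29%.

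**The case against.** The strongest reply is that little is missing. If the planned mean differences, SDs and CIs are produced in each group, the contrast is one subtraction with a standard error. The regression sentence names no variables, so it does not exclude FVL, and the plan does say that leak will be analysed. The split is pre-specified, easy for clinicians to read, and more powerful if the effect is a step near 21.1%. On the plan's own 0.5°C scale the gain from a slope is modest: 0.10°C of mean cooling implies only about 0.095°C between groups (2 × 0.798 × 12.53 × 0.10/21.1). Even at SD 0.4°C the split contrast (±0.16°C) is far narrower than 0.5°C. An unadjusted slope is also somewhat more exposed to confounding by age than the split.

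Much of this stands, and it limits the point. The contrast could be computed, both analyses have under 50% power for 0.10°C at SD 0.3°C, and the ±0.5°C verdict rule is assumed. None of it supplies a specified estimate of a leak effect. The regression sentence, read in place, concerns the two probes. The analysis of leak is qualified as means and standard deviations. A contrast chosen after seeing the data is not pre-specified. The confounding objection is a reason to report the adjusted slope beside the unadjusted one.

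**Conclusion.** The concern holds. The plan poses a question about leak size and specifies no analysis that answers it. That conclusion comes from the text and does not depend on any assumed SD or effect size.

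The size of the consequence does depend on assumptions. The 36% information loss needs roughly normal FVL, a cut near the median and a linear effect. At SD 0.3°C the gain from continuous FVL is from 29–34% to 42–49% power for 0.10°C of mean cooling, which remains low, and it reverses under a step at 21.1%. The 31–50% chance of conflicting significance results assumes equal groups of 50 and a shared bias of 0.2–0.4 SD.

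The change should be made, but the analysis is secondary. The planned precision of ±0.34 SD for the whole sample is sound, and the subgroup limits of agreement are worth keeping for the question they do answer.

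**What to change.** In Statistics and data analysis, pre-specify the following:

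1. **Leak-size analysis.** Regress the oesophageal-minus-nasopharyngeal difference with the cuff deflated on continuous FVL with the cuff deflated. Report the slope per 10 FVL points with its 95% CI and a plot, and check linearity and residual spread.
2. **Interpretation.** Report the slope unadjusted and adjusted for age or height. Call it an association, because the leak is titrated to an audible level and may vary with the child's age or size.
3. **Subgroups.** Keep bias and limits of agreement either side of 21.1% as secondary, state their wider CIs (about ±0.48 SD at 50 per group), and add the between-group mean difference with its 95% CI. Assign a value of exactly 21.1% to one group; at present it falls in neither.
4. **Inference.** State that no leak effect will be inferred from separate subgroup verdicts.
5. **Optional support.** Add the within-child change from cuff inflated to cuff deflated as a separate analysis.

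The cost is a few sentences and slightly more analysis. Both probe temperatures, the tidal volumes needed for FVL, age and height are already to be recorded (Patient management and intervention; Data collection). The downsides are a linearity assumption to check, lower power than the split if the true effect is a step near 21.1%, and a slope that remains an association even after adjustment.

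### The planned leak-size comparison splits children at FVL 21.1% without accounting for child size, which may be related to both FVL and the temperature gap

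*Combined protocol and SAP*

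**What the plan says.** The Background gives the mechanism under study: gas escaping past the tube is cooler than the body, and "these gases could possibly have a cooling effect on temperature in the nasopharynx". Under Patient management and intervention, fresh gas flow is the same for every child, the ventilator delivers "a tidal volume of 7 – 9 ml/kg", and the cuff is then let down until the anaesthetist hears a soft leak. No target volume or FVL is set for that step. The inclusion criteria span "Age: 8 months to 7 years".

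Under Statistics and data analysis, FVL is expected to have an interquartile range of 12.4 to 29.3%. The one analysis of leak size examines agreement in two subgroups divided at FVL 21.1%, to "determine if there is any potential effect of leak size that might affect temperature differences". It names no size covariate or stratification, and otherwise leak is only tabulated as means and SDs. The regression mentioned there belongs to the comparison of the two sites and has no leak or size term.

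Data collection lists "Demographics – including date of procedure, date of birth, age, height, ASA status", and inspired and expired tidal volumes over 20 breaths with the cuff inflated and deflated.

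**The concern.** FVL is a percentage of a tidal volume that scales with weight, so the same FVL is a larger volume of escaping gas in a larger child. The leak is also set by ear. If a soft audible leak is roughly the same volume of gas in any child, small children will tend to have high FVL and large children low FVL. The two groups would then differ in child size as well as in leak.

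That matters only if the gap between the two sites also varies with size. If it does, an unadjusted comparison credits part of the size effect to leak. Depending on the direction, it can create an apparent leak effect or cancel a real one. At stake is the answer to the leak-size question, which readers would use to judge whether nasopharyngeal probes can be trusted when the leak is larger.

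**Working it through.** **1. The plan's own precision figure.** The plan states that "100 patients would suffice to be able to estimate agreement between methods", with a 95% CI of 0.34 SD either side. The Bland-Altman CI for a limit of agreement gives 1.96 × √(3/100) = 0.339 SD, so the figure reproduces. It concerns overall agreement only. With 50 children per leak group (an even split is assumed), the half-width is 1.96 × √(3/50) = 0.48 SD for each limit, and 1.96 × √(1/50 + 1/50) = 0.39 SD for the difference between group means. At an assumed SD of 0.25°C the latter is about 0.10°C.

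**2. What one FVL means in different children.** Leak per breath = weight × ml/kg × FVL. The documents give no weights, so these are assumptions, at 8 ml/kg and FVL 21.1%:
- 8 kg: 8 × 8 × 0.211 = 13.5 ml; 23 kg: 23 × 8 × 0.211 = 38.8 ml; ratio 2.9.
- 9 kg: 15.2 ml; 20 kg: 33.8 ml; ratio 2.2.

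**3. Could the groups differ in size?** Suppose a soft audible leak is a similar absolute volume at any size (log-SD 0.4) and weights are uniform over 8 to 23 kg. By simulation, mean weight is then 17.6 kg in the low-FVL group and 13.3 kg in the high-FVL group, a standardised difference of about 1.0 (about 0.8 for 9 to 20 kg). This shows that imbalance is possible, not that it will occur.

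**4. Size of the false difference.** Let the gap change by b °C per SD of size, let FVL correlate r with size, and let leak have no true effect. For normal variables split at the median, the group means of size differ by 2√(2/π) × r = 1.596r SD, so the false difference is 1.596 × b × r. Signs are ignored. The table adds the rejection rate of a 5% t-test from 4,000 simulated trials of 100 children with residual SD 0.25°C. The plan does not specify that test; it is used here only as a yardstick.

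| b (°C per SD) | r | False difference (°C) | Rejection, unadjusted | Rejection, adjusted for size |
|---|---|---|---|---|
| 0.10 | 0 | 0 | about 5% | about 5% |
| 0.10 | 0.1 | 1.596 × 0.10 × 0.1 = 0.016 | about 6% | about 5% |
| 0.10 | 0.3 | 1.596 × 0.10 × 0.3 = 0.048 | about 14% | about 5% |
| 0.15 | 0.5 | 1.596 × 0.15 × 0.5 = 0.120 | about 54% | about 5% |

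The last two rows are about half to slightly more than the 0.10°C half-width in step 1.

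**5. If FVL is unrelated to size but absolute leak is the true driver.** FVL SD is taken as (29.3 − 12.4)/1.349 = 12.5 points around 20.85%, with weights uniform over 8 to 23 or 9 to 20 kg. FVL then correlates 0.84 to 0.89 with absolute leak, and 14 to 18% of children change group if split at median absolute leak instead. The FVL split keeps about 88 to 92% of the leak contrast that the absolute split would give. With a true effect of 0.10°C per SD of leak and residual SD 0.25°C, power is 77 to 80% rather than 87 to 88%.

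**The case against.** The strongest reply is that this is one supplementary analysis and the harm is hypothetical. Nothing in the documents shows that FVL varies with size, that the gap does, or that the SD is 0.25°C. Even the worst case above, 0.12°C, is about a quarter of the plan's 0.5°C limit. The plan states no between-group test, so the rejection rates describe a procedure nobody has promised to run. All of this stands, and it limits the point to a possible bias.

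Three stronger readings are tempting and are not supported.

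- **That the split ranks children wrongly by gas flow.** At 8 ml/kg and 20 breaths/min, a 23 kg child at FVL 12.4% leaks 23 × 8 × 0.124 × 20 = 456 ml/min, and an 8 kg child at 29.3% leaks 8 × 8 × 0.293 × 20 = 375 ml/min. But this reversal needs a weight ratio above 29.3/12.4 = 2.36. For 20 and 9 kg the figures are 397 and 422 ml/min, with no reversal. The plan also fixes no rate: 20/min is inferred from readings being "recorded over a period of 20 breath cycles (approximately 1 minute"), and a rate above about 24/min in the 8 kg child (456/18.8) removes the per-minute reversal.
- **That the split hides a real leak effect because FVL is the wrong measure.** Step 5 shows mild attenuation only.
- **That absolute flow is the right exposure.** The nasopharynx also grows with the child, so a size-relative measure is a legitimate choice.

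What survives is that size is left out of the comparison although height and age are already on the form.

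**Conclusion.** The point holds as a modest one. The only planned test of leak size ignores child size, in a design where FVL could plausibly be related to it. If the correlation is 0.3 to 0.5 and the gap changes by 0.10 to 0.15°C per SD of size, the false group difference is about 0.05 to 0.12°C; at a correlation of 0.1 or less it is negligible. These inputs, the residual SD of 0.25°C and all weights are assumptions.

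A reader might infer that the study's main conclusion is at risk. It is not: overall agreement between sites and the inflated-versus-deflated contrast are within-child comparisons, so they do not depend on how children are sorted into leak groups.

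**What to change.** Keep the 21.1% split and add two items before the data are examined.

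1. **Size-adjusted comparison.** Compare the mean oesophageal-nasopharyngeal difference during cuff deflation between the two FVL groups by linear regression, with group and height (or age) as terms. Report the adjusted and unadjusted differences with 95% CIs. This is a free improvement: the variables are already collected. Using mean differences avoids having to define adjusted limits of agreement.
2. **Absolute leak as a secondary description.** Calculate mean inspired minus mean expired volume, in ml per breath, from the spirometry already recorded. Show its relation to the temperature difference, without size adjustment, beside the FVL result. The cost is one more secondary result, to be read as descriptive because it mixes leak with size.

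A weight-adjusted analysis of absolute leak would add little: absolute leak is roughly FVL × weight × a constant, so on the log scale adjusting for weight returns the weight-adjusted FVL coefficient. Leak in ml/kg/min should be left out, because it equals FVL × 7 to 9 ml/kg × rate and is close to FVL rescaled.
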